### **5.3 Observation Time during Influenza Season**

For the primary objective of estimating the incidence of influenza-associated respiratory hospitalizations and ARI outpatient encounters, the person-time at risk for the underlying cohort will be needed. Person-time at risk for influenza will be calculated for all individuals in the seasonal retrospective cohorts. Observation time for a given season will start on the day that influenza season begins, September 1 of each year. For the same season, observation time will end on the day of death, disenrollment, move away from the catchment area, or the end of the influenza season (May 31), whichever occurs first. The total observation time, person-time, is then the difference between the start and end of observation. For analyses, observation time may be restricted to a shorter period of time when influenza viruses are known to be circulating in the communities surrounding the collaborating sites. Final determination for analysis will be made by group consensus.

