### **5.4 Exposures of Interest**

#### ***Vaccination status***

Within each annual retrospective cohort, an individual will be considered vaccinated for influenza if there is documented evidence of influenza vaccination and evidence that the vaccination was administered at least two weeks prior to an influenza-associated respiratory hospitalization (or influenza-associated ARI outpatient visit).

In order to assess influenza vaccination status, multiple sources will be queried, as available, including EHR, state/local vaccine registries, all-payer claims or other billing databases. For each available source, data will be provided on date of vaccination, type of vaccine administered, vaccination route, location of vaccination, vaccine lot number and number of vaccine doses (for children <9 years of age). Vaccination records will be considered as evidence of vaccination if there is at least a partial date (month and year). Children (aged <9 years) will be considered fully vaccinated for the current season if they received two doses, at least one month apart, during the current season or if they received one dose of the current season's vaccine and had at least two doses in prior seasons.

Network sites will provide information on number of sources queried for vaccine data and completeness of data by vaccine source. Because each site is querying multiple sources, a hierarchy of sources will be established for each site or through joint consensus with collaborating partners. For vaccination data extracted from EHRs, sites will provide information on how vaccination data was pulled (for example, through use of CPT or other codes).

For a subset of patients (number to be determined by joint consensus by the collaborating partners), accuracy of extracted vaccination data will be verified through manual review of source data (i.e. medical chart review).

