***Objective 4: Measure incidence of health outcomes related to influenza***

- Incidence of laboratory-confirmed influenza-associated respiratory hospitalizations will be calculated by dividing the number of respiratory hospitalizations associated with a positive influenza laboratory test observed during each study season by the person-time of the cohort at risk during the corresponding season.
  - This will be calculated for the following risk groups: age group, high-risk conditions, vaccinated for influenza, unvaccinated, race/ethnicity, socio-economic status, etc.
  - Incidence will be compared between risk groups using rate differences or relative rates

- Incidence of ICU admission, mechanical ventilation, and in-hospital death associated with influenza will be similarly calculated, with the respective numerators restricted to those laboratory-confirmed influenza-associated respiratory hospitalizations with the relevant outcomes identified.
  - This will be calculated for the following risk groups where sample size permits: age group, high-risk conditions, vaccinated for influenza, unvaccinated, race/ethnicity, socio-economic status, etc.
  - Incidence will be compared between risk groups using rate differences or relative rates
- Incidence of laboratory-confirmed influenza-associated acute respiratory illness (ARI)-associated outpatient visits will be calculated by dividing the number of ARI visits with a laboratory test positive for influenza observed during each study season by the person-time of the cohort at risk during the corresponding season.
  - This will be calculated for the following risk groups where sample size permits: age group, high-risk conditions, vaccinated for influenza, unvaccinated, race/ethnicity, socio-economic status, etc.
  - Incidence will be compared between risk groups using rate differences or relative rates

As multiple events are possible during a season, incidence estimates throughout this objective may be calculated in two ways: 1) counting only the first occurrence, and 2) counting the cumulative number across the season.

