  - Controls will be defined as hospitalized individuals who tested negative for influenza.
  - Influenza vaccination status will be determined for all cases and controls and the odds of vaccination will be compared using logistic regression.
  - VE will be estimated as  $(1 - \text{adjusted odds ratio}) \times 100$ .
  - We will assess and adjust for confounders as appropriate. This may include characteristics such as age group, sex, site, race/ethnicity, high-risk health conditions, prior healthcare utilization, time of event during the influenza season, etc.
  - Data collected for this study are intended to be pooled across sites. VE will first be estimated for each site and heterogeneity in estimated VE across sites will be examined.

Beyond the primary objectives listed here, additional analyses may be pursued and will be considered by the joint steering committee.

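### Objective 4 rates by vaccination status: an outcome-anchored definition on unsplit person-time biases the vaccinated-versus-unvaccinated comparison toward the vaccine

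*Protocol*

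**What the plan says.** Three parts of the protocol bear on this.

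- **Section 5.4, Vaccination status.** The label belongs to the person: "an individual will be considered vaccinated for influenza if there is documented evidence of influenza vaccination". A timing condition is attached to that label, and it is tied to the outcome: "evidence that the vaccination was administered at least two weeks prior to an influenza-associated respiratory hospitalization (or influenza-associated ARI outpatient visit"). No reference date is given for a cohort member who has no influenza event.
- **Section 5.3, Observation Time.** "Observation time for a given season will start on the day that influenza season begins, September 1 of each year". It ends at death, disenrollment, a move out of the catchment area or May 31. "The total observation time, person-time, is then the difference between the start and end of observation". There is no split at vaccination or at vaccination + 14 days. The section adds that "observation time may be restricted to a shorter period of time when influenza viruses are known to be circulating", with the decision left to group consensus.
- **Section 6.1, Objective 4.** Events are divided by the season person-time of the cohort. "This will be calculated for the following risk groups: age group, high-risk conditions, vaccinated for influenza, unvaccinated, race/ethnicity, socio-economic status, etc". Then: "Incidence will be compared between risk groups using rate differences or relative rates". Section 1.5 also plans rates stratified by current-season vaccination status.

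Exposure that varies over time is specified only in section 6.1, Objective 5, for the cohort analyses of vaccine effectiveness. The test-negative analysis under Objective 5 says that "Influenza vaccination status will be determined for all cases and controls" and does not say as of what date.

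**The concern.** Vaccination happens during follow-up, so a person who is vaccinated in November has been at risk, unvaccinated, since September 1. On a literal reading of sections 5.3, 5.4 and 6.1 together, what happens to that early time depends on the outcome. If the person has an influenza hospitalization before dose + 14 days, the event goes to the unvaccinated group. If not, the whole season, including the weeks before the dose, goes to the vaccinated group. The vaccinated group thus gains person-time in which, by construction, it cannot have an event, and the unvaccinated group gains events without the matching person-time.

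Objective 4 is a primary objective. Its relative rate by vaccination status could show a benefit for an ineffective vaccine and could differ from the Objective 5 estimate obtained from the same records. The distortion would also vary between seasons, being larger when the epidemic is early, and so could affect comparisons of seasons.

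**Working it through.** The protocol states no figure for this comparison, so there is none to reproduce.

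**Inputs from the protocol (section 6.2)**
- Adult coverage: 30%, 42% and 65% in three equal groups, so c = (0.30 + 0.42 + 0.65)/3 = 0.457.
- Child coverage: 70% and 50% in two equal groups, so c = 0.60.

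**Assumed input**
- q, the share of eventual vaccinees' influenza risk that falls before dose + 14 days. The protocol gives neither an uptake curve nor an epidemic curve, so q is varied from 0.01 to 0.20.

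**Formula.** Let R be the season risk without vaccination, equal in both groups apart from the vaccine effect. Events are rare, so c is hardly changed by relabelling early cases.
- Vaccinated: events c(1−q)(1−VE)R on person-time proportional to c.
- Unvaccinated: events (1−c)R + cqR on person-time proportional to 1−c.
- Observed rate ratio = (1−VE)(1−q) / [1 + q·c/(1−c)].

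The factor (1−q)/[1 + q·c/(1−c)] is below 1 for every q > 0, so the bias always favours the vaccine. The ratio c/(1−c) is 0.8405 for adults and 1.5 for children. Example, adults, q = 0.10: 0.90/1.084 = 0.830, an apparent effectiveness of 17.0% when the true value is 0.

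| q | Adults, true VE 0 | Adults, true VE 40% | Children, true VE 0 |
|---|---|---|---|
| 0.01 | 1.8% | 41.1% | 2.5% |
| 0.05 | 8.8% | 45.3% | 11.6% |
| 0.10 | 17.0% | 50.2% | 21.7% |
| 0.20 | 31.5% | 58.9% | 38.5% |

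**Which q is plausible?** A day-by-day calculation over 273 days for adults used assumed normal curves: uptake centred in mid-October (SD 30 days) or early November (SD 40), and an epidemic peak in late December, early January or early February (SD 28). It gave q from 0.009 to 0.222 and an apparent effectiveness under no effect of 1.7% to 34.5%. Restricting the window to the central 90% of the epidemic left 0.8% to 32.6%.

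The result is sensitive to the assumed spreads. With uptake centred on day 45 or 60, both coverages, and SDs of 15 to 30 days for each curve, a peak on day 120 gave from under 1% to 29%, and a peak on day 160 gave from 0% to 5%.

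**Does splitting the person-time cure it?** Not alone. In the six adult scenarios, a crude whole-season ratio on correctly split person-time gave an apparent effectiveness of −16% to −61% under no effect, because unvaccinated time is concentrated in the low-incidence autumn. In the grid with SDs of 15 to 30 days and peaks on days 100 to 160, the crude split ranged from about −1% to below −90%. Splitting and comparing within calendar day returned 0.0% in every scenario.

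**The case against.** The best defence is that nothing in the protocol says status is fixed for the season. Objective 4 does not state how person-time is divided between vaccinated and unvaccinated, vaccination dates are collected, and Objective 5 treats the same exposure as varying over time. Allocation of person-time is often left to a statistical analysis plan. Vaccination status is also absent from the stratifiers in the section 4.1 statement of Objective 4 and from its row in Appendix A. It appears in a list in section 6.1 and in section 1.5.

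Part of this stands. The fixed grouping is a reading of three sections together, and the contrast is one of several under an incidence objective. But the point is not that a detail is missing: section 5.4 states an outcome-anchored rule, section 5.3 states an unsplit person-time rule, and section 6.1 commits to the comparison. The possible shorter window is optional and, in the scenarios above, removed little of the bias.

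A reader might infer three stronger things that the protocol does not support.

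- *That the vaccine effectiveness estimates are biased.* The Objective 5 cohort analyses are specified with time-varying exposure, which protects them.
- *That test-negative controls have no reference date.* All subjects in that analysis were hospitalized, so each has an admission date, and no person-time is involved. The only defect is that section 5.4 ties status to an influenza-associated event, which controls by definition lack.
- *That a particular size of bias can be stated.* It cannot, because the overlap of uptake and circulation is not given.

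**Conclusion.** The point holds for the Objective 4 vaccinated-versus-unvaccinated rates and their ratios or differences, including the outcomes for which Objective 4 repeats the same grouping. On the literal reading the direction is certain: toward the vaccine. The size is not. It rests on the assumed q and on the section 6.2 coverages. For q of 0.01 to 0.20, an ineffective vaccine appears about 2% to 32% effective in adults and 2.5% to 39% effective in children. If nearly all vaccination precedes circulation, the bias is close to zero. The test-negative analysis needs a wording correction only. This should be fixed, but it does not undermine the study's vaccine effectiveness estimates.

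**What to change.** - **Section 5.4.** Define status by calendar day for every cohort member, with or without an event: unvaccinated before the dose, vaccinated from day 14, and days 0–13 either counted as unvaccinated or kept as a separate category. State which.
- **Incomplete dates.** Section 5.4 accepts month-and-year records, for which day 14 cannot be computed. Add a rule, for instance an assigned day within the month with a sensitivity analysis at the earliest and latest possible day.
- **Children under 9.** Word the day-based status so that it agrees with the two-dose definition already in section 5.4.
- **Section 6.1, Objective 4.** Split both person-time and events by that status, and compare rates within, or adjusted for, calendar time. This second part is essential, because a crude split biases against the vaccine.
- **Test-negative analysis.** Reword only: status is taken at the admission date for cases and controls alike.

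The cost is a calendar-stratified person-time table for the Objective 4 vaccination contrasts, across its hospitalization, ICU, ventilation, death and outpatient rates, plus the rewording. Objective 5 already requires the same split, so no new data are needed.

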## **1.5 Methods Summary**

To fulfill the network aims each site will construct patient cohorts based on care seeking and if possible health insurance enrollment criteria and extract select demographic, health system utilization, medical, laboratory, pharmaceutical, and vaccination records from electronic health

records for each retrospective study period. Study periods are defined by influenza seasons. Each site will determine the number of years for which they will contribute data, or the period of time in which records are robust enough for cohort identification, beginning as early as the 2010/11 influenza season.

Retrospective cohorts will be defined among individuals within the health system who would visit an outpatient provider or would be hospitalized within the health system if s/he had an influenza virus infection that required hospitalization. A cohort will be defined for each influenza season during the retrospective surveillance period. Influenza season will be broadly defined from September 1 of a year through May 31 of the following year. For analysis, influenza seasons can be more narrowly defined by the frequency of influenza positive test results within the health system. Separate pediatric and adult cohorts will be defined.

For each individual in each of the cohorts, information will be extracted from medical and public health records. Each site will contribute individual-level, but limited, data for the primary analytic objectives. For assessing risk of influenza-associated outcomes, we expect to calculate rates of influenza-positive respiratory hospitalizations among persons at risk of influenza during the season. We intend to calculate rates stratified by age group, high risk underlying conditions, current season vaccination status, current and prior season vaccination status, and other stratifications as suggested by the collaborating network. We will further estimate influenza vaccine effectiveness against influenza-associated respiratory hospitalization and other associated outcomes, both overall and stratified by high-risk conditions. Possible further analytic objectives may be pursued given resources and successful completion of the primary objectives.

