## **5.0 Methods**

### **5.1 Study Design**

All sites will define retrospective seasonal cohorts of adults and children, which are intended to include all individuals within the health system who would be hospitalized or seek outpatient care within that health system if they had an influenza virus infection that required hospitalization. Among all individuals in the retrospective cohort, medical, laboratory, and vaccination records will be extracted to assess the primary study objectives.

The influenza season will be defined as the time between September 1 of a year and May 31 of the subsequent year. For example, the 2015–2016 influenza season begins on September 1, 2015 and ends after May 31, 2016. Each study site will determine the number of previous influenza seasons (considering seasons between 2010/11 and 2018/19) for which their site will contribute data, depending on the availability and quality of electronic health record (EHR) data in their health system. Adult and pediatric cohorts will be analytically defined for each influenza season for which a site contributes data. Cohorts will be followed up for the duration of each influenza season to meet the primary objectives.

Figures 1 and 2 display the high-level study design for the primary hospitalization and outpatient outcomes, respectively.

Figure 1. High-level study design for hospitalization outcomes

[figure not shown]
[figure not shown]

Figure 2. High-level study design for outpatient outcomes

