## **5.6 Summary of Data Elements for Primary Objectives**

Please see Appendix B for more detailed list of data elements

[figure not shown]
- For the entire cohort:

- Demographic information (age, sex, race, ethnicity)
- Date of enrollment in health plan and/or date of first encounter in the health system in the 12 months before the start of influenza season (as applicable)
- Healthcare utilization (primary/secondary insurance type, number of medical encounters before and during influenza season). This is further defined to be the monthly number of healthcare encounters by setting (general practice, medical specialty, emergency department, urgent care, telehealth, or inpatient).
- Underlying high risk medical conditions (derived from ICD codes)
- Vaccination status (influenza and other vaccinations received dating back to 2010)
- All hospitalizations and outpatient encounters with respiratory virus testing during influenza season of interest:
  - Date of encounter (or date of admission)
  - Date of testing
  - Clinical setting
  - Influenza and other respiratory virus test type and result
  - Diagnosis codes from the encounter/admission
- Respiratory syndrome-associated hospitalizations during influenza season of interest:
  - Hospital admission and discharge dates
  - Diagnosis codes
  - Severe outcomes (ICU admission, mechanical ventilation, in-hospital mortality)
- ARI syndrome-associated outpatient encounters during influenza season of interest
  - Encounter date
  - Diagnosis codes

Data streams for entire cohort during to-be-determined lead-in period:

[figure not shown]

Data streams for influenza season of interest:

[figure not shown]

All sources should be linked by subject ID  
 \*For influenza and other vaccinations received dating back to 2010, where possible.

Data streams for entire cohort during to-be-determined lead-in period:

Data streams for influenza season of interest:

All sources should be linked by subject ID  
 \*For influenza and other vaccinations received dating back to 2010, where possible.

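### For one-dose children under 9, the prior-dose route to fully vaccinated cannot be evaluated correctly in the earliest seasons, because records are requested only back to 2010

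*Protocol*

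**What the plan says.** Section 5.4 (Vaccination status) gives children under 9 two routes to being fully vaccinated. The first applies "if they received two doses, at least one month apart, during the current season" and needs no earlier history. The second applies to a child who received one dose this season "and had at least two doses in prior seasons", so it does need that history.

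The extraction window is set elsewhere. The note to the data-stream figure in section 5.6 reads "For influenza and other vaccinations received dating back to 2010, where possible", and Appendix E repeats that limit. Section 1.5 has sites contribute seasons "beginning as early as the 2010/11 influenza season", and section 5.1 gives the range as "considering seasons between 2010/11 and 2018/19", with each site choosing by the availability and quality of its electronic records. Depth of dose history is not named as a condition for contributing a season. Section 5.4 sets no minimum look-back and no rule for a one-dose child whose earlier history predates the records.

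**The concern.** The request starts in the same calendar year as the first permitted cohort, while the second route needs doses from earlier seasons. In 2010/11 only January to August 2010 can be seen before the season opens. The second route then almost disappears, and fully vaccinated comes close to meaning two doses this season. The category regains its written meaning only as look-back grows.

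This affects work that the protocol plans. Section 4.1, Objective 2, makes the validity of vaccination data for current and prior seasons a primary aim and lists the number of doses in children under 9. Section 4.2 includes a secondary objective on how the number and timing of priming doses in children relate to later vaccine effectiveness (VE). The chart validation in Appendix G samples by vaccinated and unvaccinated status and checks vaccination status, not completeness of earlier doses, so it is not designed to reveal the gap. Doses that were never extracted cannot be recovered at the analysis stage.

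**Working it through.** The protocol gives no figure on this point, so there is none to reproduce.

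**Inputs from the protocol:** season start 1 September (5.1); seasons 2010/11 to 2018/19 (5.1); records from 2010, month not stated (5.6); vaccination from age 6 months (3.1); coverage 70% at 6 months to 4 years and 50% at 5 to 17 years (6.2).

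**Assumptions not in the protocol:** ages uniform from 0.5 to under 9 years; complete capture once records begin; record start 1 January 2010, with 1 September 2010 as a variant.

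**Step 1: what the dates alone imply.** Take a primed child who gets one dose every autumn. Visible prior doses number 0 in 2010/11 (the autumn 2009 dose predates the records), 1 in 2011/12 and 2 in 2012/13. The second route first works for this child in 2012/13.

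**Step 2: share with possibly truncated history.** History may be truncated if the child reached 6 months before records began. For the season starting in year Y, that means age above a = (Y + 8/12) − 2010 + 0.5, and the share is (9 − a)/8.5.
- 2010/11: a = 1.17, (9 − 1.17)/8.5 = 92%.
- 2013/14: a = 4.17, (9 − 4.17)/8.5 = 57%.
- 2018/19: a exceeds 9, so 0%.

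**Step 3: ceiling on misclassification.** A child with no current-season dose is not fully vaccinated whatever the history, so only truncated and vaccinated children can be misclassified. Their share of all children is [0.7 × max(0, 5 − a) + 0.5 × (9 − max(a, 5))]/8.5. For 2010/11 this is (0.7 × 3.83 + 0.5 × 4)/8.5 = 55%.

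**Step 4: simulated misclassification.** An error needs exactly one current dose, at least two true prior doses, and fewer than two of those recorded. Further assumptions: probability 0.3, 0.6 or 0.9 of a second dose in any season with fewer than two prior doses; between-season correlation of vaccination 0, 0.5 or 0.95; constant coverage; all doses placed in mid-October. The last assumption ignores doses given from January to August 2010, so it somewhat overstates the first seasons. Ranges run over the nine combinations.

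| Season | Truncated, records from 1 Jan 2010 | Truncated, records from 1 Sep 2010 | Ceiling, all children (1 Jan) | Simulated error, all children | Simulated error, vaccinated children |
|---|---|---|---|---|---|
| 2010/11 | 92% | 100% | 55% | 41–51% | 69–85% |
| 2011/12 | 80% | 88% | 47% | 37–43% | 62–72% |
| 2012/13 | 69% | 76% | 39% | 3–20% | 5–33% |
| 2013/14 | 57% | 65% | 30% | 1–9% | 2–15% |
| 2014/15 | 45% | 53% | 23% | about 3% or less | about 5% or less |
| 2015/16 | 33% | 41% | 17% | 1% or less | under 2% |
| 2016/17 | 22% | 29% | 11% | not run | not run |
| 2017/18 | 10% | 18% | 5% | not run | not run |
| 2018/19 | 0% | 6% | 0% | not run | not run |

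The truncated shares fall slowly and the simulated error falls fast, because two visible prior doses are enough and a lifetime history is not needed.

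**The case against.** The strongest reply is that no primary analysis uses the fully vaccinated category. Section 5.4 defines vaccinated by documented vaccination at least two weeks before the event, with no prior-dose condition. Section 6.1, Objective 5, compares members with and without current-season vaccination, and its test-negative analysis compares odds of vaccination. This stands. A reader might infer that paediatric VE is biased toward the null, or that primed children slip into the unvaccinated group. The protocol supports neither: a one-dose child who meets the two-week rule is vaccinated whatever the history, and no partial group is defined.

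The direction argument also stands. Because only truly full children are misplaced, the recorded full group is not contaminated by partial ones. A full-versus-none estimate need not shrink if the error is unrelated to outcome. Only a contrast of full with partial, or with not full, is diluted.

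A reader might also infer drift in an estimate pooled over seasons. Section 6.1 states pooling across sites, and cohorts are built season by season.

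Other replies carry less weight. Sites may decline early seasons, but on grounds of record quality, with no mention of dose look-back. Section 5.4 asks each source for the number of doses in children under 9 without a date limit in that sentence, but section 5.6 and Appendix E impose one. Section 5.7 leaves methods for the secondary objectives to later amendment, and the Appendix B codebook is not at hand. Neither changes the extraction window that the protocol does state.

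**Conclusion.** The point holds for one-dose children under 9 in the earliest seasons. The written rule and the written extraction window together give wrong full-vaccination status, mainly in 2010/11 and 2011/12, with less error in 2012/13 and little by 2014/15. The error runs one way, from full to not full. Its reach is the full/not-full classification, any full-versus-partial contrast, and the prior-dose data behind Objective 2 and the secondary priming-dose objective. Primary VE for any current-season vaccination versus none is untouched.

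The series from 92% to 0% should not be read as a misclassification rate. It is the most that can be affected, given uniform ages and complete capture from 1 January 2010. Children with no current dose, two qualifying current doses or two recorded prior doses are classified correctly. A majority is misclassified only among vaccinated children, only in the first two seasons, and only under the simulation's assumptions. That the second route fails in those two seasons for a child dosed once each autumn follows from the protocol's dates alone.

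**What to change.** In section 5.6 and Appendix E, request influenza doses for children under 9 back to birth wherever the electronic record or registry allows.

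Where it does not, add a rule to section 5.4. A child with one current-season dose, a history that may predate the source's records, and fewer than two recorded prior doses is classed as *priming unknown* and left out of full/partial contrasts. Children verifiably full through two current-season doses or two recorded prior doses stay in. A plain birth-date cut-off would be simpler but would discard those verifiable children. Any-dose analyses keep everyone.

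The cost is a wider date range in the query, or a short rule in section 5.4, and fewer children in early-season full/partial contrasts. The wider request has to be made before extraction to be of use.
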